#### 3.7.2 Diarrhea

Antidiarrheal medications will not be used prophylactically; however, patients will be instructed to take loperamide, 4 mg, at the occurrence of the first loose stool and then 2 mg every 2 hours until they are diarrhea-free for at least 12 hours. During the night, patients may take 4 mg of loperamide every 4 hours. Fluid intake should be maintained to avoid dehydration.

#### 3.7.3 Central Nervous System Effects

If a patient experiences excessive sedation believed to be related to alisertib, treatment with alisertib should be interrupted. Patients whose sedation is not considered immediately lifethreatening should be carefully monitored and given appropriate supportive care.

### 3.7.4 Treatment Compliance

All drug(s) will be administered to eligible patients under the supervision of the investigator or identified sub-investigator(s). The research staff will maintain records of drug receipt (if applicable), drug preparation, and dispensing, including the applicable lot numbers, patients' height, body weight, and body surface area (see Section 9.5), and total drug administered in milliliters and milligrams. Any discrepancy between the calculated dose and dose administered and the reason for the discrepancy must be recorded in the source documents.

#### 3.8 Duration of Treatment and Patient Participation

Once patients register and enroll on this trial, they will be monitored per study guidelines while on treatment.

Patients enrolled and treated on this trial will continue with therapy until:

- 1) Unacceptable toxicities requiring removal from study
- 2) Disease progression defined by modified RECIST or RECIST
- 3) Patient withdraws consent
- 4) Treating physician removes patient from the trial for the reasons outlined in Section 3.9.

Once patients are taken off active treatment and begin long-term follow-up, they will be monitored for both first disease progression and overall survival.

#### 3.9 Termination of Treatment and/or Study Participation

Patients will be informed that they have the right to withdraw from the study at any time for any reason, without prejudice to their medical care. The investigator also has the right to withdraw patients from the study for any of the following reasons:

- Intercurrent illness
- Occurrence of an unacceptable adverse event
- A treatment cycle delay or alisertib interruption of 2 weeks because of toxicity
- Patient request

- Protocol violations
- Non-compliance
- Administrative reasons
- Failure to return for follow-up
- General or specific changes in the patient's condition unacceptable for further treatment in the judgment of the investigator
- Progressive disease at any time

At the time of withdrawal, all study procedures outlined for the End of Study visit should be completed. The primary reason for a patient's withdrawal from the study is to be recorded in the source documents.

#### 3.10 Efficacy and Safety Measurements

#### 3.10.1 Efficacy Measurements

Patients will be re-staged every 2 cycles of therapy (6 weeks). 1 cycle = 21 days or 3 weeks. Imaging studies will consist of any of the following studies: PET-CT scans, chest CT scans, abdominal-pelvic CT scans. Modified RECIST (preferred) or RECIST (if modified RECIST cannot be used) measurements will be performed after every 2 cycles of therapy. The radiologist or the PI will review and determine response based on the RECIST. Examples of these measurements are described in Tsao et al.[1]

#### 3.10.2 Safety Measurements

Patients will be evaluated with a history and physical exam during each clinic visit. Baseline laboratory values will be obtained during each clinic visit. All toxicities reported will be recorded by the research RN and graded using the National Cancer Institute Common Terminology Criteria for Adverse Events (NCI CTCAE), Version 4.03, effective 14 June 2010 (16). These criteria are provided in the Study Manual and are available online at http://ctep.cancer.gov/protocolDevelopment/electronic\_applications/ctc.htm.

#### 3.11 Study Drug Administration

Alisertib will be administered PO at 50 mg BID for 7 days in each treatment cycle, followed by a 14-day, treatment-free period.

Patients will be instructed to take each oral dose of alisertib with 8 ounces (1 cup, 240 mL) of water. For BID dosing, the doses must be taken at least 6 hours apart.

Alisertib will be supplied as 10 mg ECT, with the dose strength expressed as milligrams of active drug (free acid); higher strengths may be supplied depending on the observed MTD. All tablets are to be ingested whole; patients who have difficulty swallowing tablets will be excluded from the study. Antiemetogenic agents may be administered at the discretion of the investigator. Although not prohibited, the use of benzodiazepines for the prophylaxis or treatment of nausea or vomiting is discouraged because of the potential benzodiazepine-like effects of alisertib.

Study drug will be administered only to eligible patients under the supervision of the investigator or identified subinvestigator(s).

### 3.12 Description of Investigational Agents

Alisertib drug product is supplied as the ECT dosage form in 10 mg strengths with dose strength expressed as the milligrams of active drug (free acid); other strengths may be supplied based on the observed MTD. The key formulation excipients of the alisertib tablet formulation that aid in the in vivo absorption of the drug are the buffer (sodium bicarbonate), the surfactant (sodium lauryl sulfate), and the enteric coating.

#### 3.13 Preparation, Reconstitution, and Dispensation

Alisertib ECT are packaged (10 tablets to a bottle) in a 60-cc high-density polyethylene (HDPE) bottle with a child-resistant cap.

Alisertib is an anticancer drug, and as with other potentially toxic compounds, caution should be exercised when handling alisertib. It is recommended that gloves and protective garments be worn during preparation.

#### 3.14 Packaging and Labeling

The packaged and labeled study drug, alisertib ECT, will be provided by Millennium and will be handled at the investigative site as open-label material. The labels on the study drug will fulfill all requirements specified by governing regulations. Ten alisertib ECT are packaged into each 60-cc HDPE bottle. Alisertib will be supplied as ECT in 10 mg or 50 mg strengths. The bottles will have a child-resistant cap and be labeled for take-home use. Patients will receive instructions for home use of alisertib, including the requirement that alisertib be administered as intact tablets.

As required by local regulations, any modifications to the plan for drug supply or storage will be communicated to the investigator and detailed in the Study Manual.

#### 3.15 Storage, Handling, and Accountability

Tablets should remain in the bottle provided until use. The container should be stored at the investigative site at controlled room temperature (20-25°C; 68-77°F; excursions are permitted from 15-30°C; 59-86°F) and used before the retest expiry date provided by Millennium. Containers should be kept closed during storage.

Because alisertib is an investigational agent, it should be handled with due care. In case of contact with broken tablets, raising dust should be avoided during the cleanup operation.

The product may be harmful by inhalation, ingestion, or skin absorption. Gloves and protective clothing should be worn during preparation and the cleanup operation. The area should be ventilated and the spill site washed after material pick-up is complete. The spilled material should be disposed of as hazardous medical waste in compliance with federal, state, and local regulations.

In case of contact with the powder (eg, from a broken tablet), skin should be washed immediately with soap and copious amounts of water for at least 15 minutes.

In case of contact with the eyes, copious amounts of water should be used to flush the eyes for at least 15 minutes. Medical personnel should be notified.

Patients are to be instructed on proper storage, accountability, and administration of alisertib, including that alisertib is to be taken as intact tablets.

## 4. ADVERSE EVENTS

#### 4.1.1 Adverse Event Definition

Adverse event (AE) means any untoward medical occurrence in a patient or subject administered a pharmaceutical product; the untoward medical occurrence does not necessarily have a causal relationship with this treatment. An AE can therefore be any unfavorable and unintended sign (including an abnormal laboratory finding), symptom, or disease temporally associated with the use of a medicinal (investigational) product whether or not it is related to the medicinal product. This includes any newly occurring event, or a previous condition that has increased in severity or frequency since the administration of study drug.

For this protocol an abnormal laboratory value will not be assessed as an AE unless that value leads to discontinuation or delay in treatment, dose modification, therapeutic intervention, or is considered by the investigator to be a clinically significant change from baseline.

Adverse events are documented in the Case Report Forms (CRF) and CORe is the database for AE collection. The PI and the designees will be responsible for assigning attribution to study drug, and how this will be documented.

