#### 1.6 Study rationale and selection of drug doses

#### **Study Rationale**

There are 3 subtypes of aurora kinases (A, B, C), but only aurora kinase A and B are potential therapeutic targets. Aurora kinase A inhibition leads to mitotic delay, monopolar spindles, and chromosomal segregation errors whereas aurora kinase B inhibition causes dysfunctional cytokinesis, polyploidy, and apoptosis. Preclinical studies have strongly suggested aurora kinases to be a relevant therapeutic target in mesothelioma patients. Several independent groups have reported that aurora kinase gene expression is upregulated in mesothelioma tumor tissue and is a negative prognostic factor.[15, 16](also our group – publication pending). Crispi et al.[17] have also shown that inhibition of mesothelioma cell lines with an aurora kinase inhibitor ZM447439 led to cell growth arrest and was target specific. Kim et al. also reported on irradiated mesothelioma cells and how inhibition of surviving and aurora kinase B resulted in mitotic cell arrest.

There are several aurora kinase inhibitors under investigation. For aurora kinase A inhibitors, alisertib, (MLN8237, Millenium) are under investigation in phase I and II trials. Preliminary results suggest dose limiting toxicity to be myelosuppression and mucositis. Aurora kinase B inhibitors, GSK1070916A (GlaxoSmithKline) and AZD1152 (AstraZeneca) are also under investigation in phase I and II trials in solid tumors and AML.

Several additional phase I and II trials of pan-aurora kinase inhibitor trials are underway in solid tumors. Alisertib (International Proprietary Name, also known as MLN8237) is a selective small molecule inhibitor of Aurora A kinase that is being developed for the treatment of advanced malignancies.

To date, there are no aurora kinase inhibitor-specific mesothelioma trials and the proposed study would be the first to assess this class of drug in the disease. Based on the preclinical data reported in the literature and our own profiling studies, we believe that aurora kinase is a feasible and relevant target in mesothelioma therapeutics. Alisertib is a novel compound that has a reasonable safety profile and may show efficacy in this population of patients.

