#### 3.3.4 Dose Modifications for Hematological Toxicity

If a patient experiences any of the following hematological toxicities during the dosing period, dosing will be discontinued for the remainder of that cycle and the dose will be decreased 1 level for all subsequent cycles of treatment.

- Grade 4 neutropenia (ANC < 500 cells/mm³) lasting more than 7 consecutive days
- Grade 4 thrombocytopenia (platelet count < 25,000/ $\mu$ L) lasting more than 7 consecutive days
- Platelet count less than 10,000/μL at any time
- Grade 3 neutropenia with fever or infection, or both, where fever is defined as an oral temperature greater than 38.3°C
- Grade 3 thrombocytopenia with clinically significant bleeding

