- Clarification should be made between a serious AE (SAE) and an AE that is considered severe in intensity (Grade 3 or 4), because the terms serious and severe are NOT synonymous. The general term *severe* is often used to describe the intensity (severity) of a specific event; the event itself, however, may be of relatively minor medical significance (such as a Grade 3 headache). This is NOT the same as *serious*, which is based on patient/event outcome or action criteria described above, and is usually associated with events that pose a threat to a patient's life or ability to function. A severe AE (Grade 3 or 4) does not necessarily need to be considered serious. For example, a white blood cell count of 1000/mm³ to less than 2000 is considered Grade 3 (severe) but may not be considered serious. Seriousness (not intensity) serves as a guide for defining regulatory reporting obligations.

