## 4.2 Communication between Investigator and Millennium

AEs may be spontaneously reported by the patient and/or in response to an open question from study personnel or revealed by observation, physical examination, or other diagnostic procedures. Any clinically relevant deterioration in laboratory assessments or other clinical finding is considered an AE. When possible, signs and symptoms indicating a common underlying pathology should be noted as one comprehensive event. AEs which are serious must be reported to Millennium Pharmacovigilance (or designee) from the first dose of alisertib up to and including 30 days after administration of the last dost of alisertib. Any SAE that occurs at any time after completion of alisertib treatment or after the designated follow-up period that the investigator and/or sub-investigator considers to be related to any study drug must be reported to Millennium Pharmacovigilance (or designee). Planned hospital admissions or surgical procedures for an illness or disease that existed before the patient was enrolled in the trial are not to be considered AEs unless the condition deteriorated in an unexpected manner during the trial (e.g., surgery was performed earlier or later than planned). All SAEs should be monitored until they are resolved or are clearly determined to be due to a patient's stable or chronic condition or intercurrent illness(es).

Since this is an investigator-initiated study, the principal investigator [name], , is responsible for reporting serious adverse events (SAEs) to any regulatory agency and to the investigator's EC or IRB. Regardless of expectedness or causality, all SAEs must also be reported to Millennium Pharmacovigilance or designee as soon as possible, but no later than 4 calendar days of the investigator's observation or awareness of the event. See below for contact information for the reporting of SAEs to Millennium Pharmacovigilance.

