## 5.5 Evaluation of Safety

Patients will be evaluated with a history and physical exam during each clinic visit. Baseline laboratory values will be obtained during each clinic visit. All toxicities reported will be recorded by the research RN and graded using the National Cancer Institute Common Terminology Criteria for Adverse Events (NCI CTCAE), Version 4.03, effective 14 June 2010 (16). These criteria are provided in the Study Manual and are available online at http://ctep.cancer.gov/protocolDevelopment/electronic applications/ctc.htm.

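### Laboratory toxicities that prompted no action are recorded only on investigator judgement, and no laboratory-based grade table is planned, so some cytopenia and liver-test rates may be understated

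*Combined protocol and SAP*

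**What the plan says.** **AE rule.** Section 4.1.1 opens with a broad definition covering "any unfavorable and unintended sign (including an abnormal laboratory finding), symptom, or disease temporally associated". It then narrows this for the present protocol: "an abnormal laboratory value will not be assessed as an AE unless that value leads to discontinuation or delay in treatment", with the further routes "dose modification, therapeutic intervention, or is considered by the investigator to be a clinically significant change from baseline". Section 4.2 has its own wording: "Any clinically relevant deterioration in laboratory assessments or other clinical finding is considered an AE".

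**Safety evaluation.** Toxicity is a secondary objective. Section 5.5, matching Section 3.10.2, states: "All toxicities reported will be recorded by the research RN and graded using the National Cancer Institute Common Terminology Criteria for Adverse Events". Neither it nor the descriptive methods in Section 5.1 plan a summary derived from laboratory values.

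**Action rules.** Section 3.3.3 delays a cycle if ANC is below 1,500/mm³ or platelets are below 75,000/mm³. Section 3.3.4 changes the dose for Grade 4 neutropenia or thrombocytopenia only when "lasting more than 7 consecutive days", for platelets below 10,000/µL, and for Grade 3 neutropenia with fever or infection or Grade 3 thrombocytopenia with significant bleeding. Section 3.3.5 covers drug-related Grade 3 non-haematological toxicity, with exceptions, and related Grade 2 toxicity when the investigator thinks a reduction is needed. It also has a general sentence on stopping for Grade 4 toxicity.

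**Expected toxicity and data.** Section 1.5 lists leukopenia, lymphopenia, anaemia and abnormal liver tests among observed risks. Section 1.6 says: "Preliminary results suggest dose limiting toxicity to be myelosuppression and mucositis". The Protocol Summary lists laboratory values as safety data. The Schedule of Events places blood counts, bilirubin, AST, ALT, electrolytes and creatinine clearance at prestudy and on cycle Day 1.

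**The concern.** The AE rule has no grade threshold. A severe laboratory abnormality that prompted no action becomes an AE only if the investigator judges it significant. Section 4.2 adds a second judgement test in different words, not a threshold.

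In an open-label, single-institution trial the toxicity table would then partly measure how often staff acted or judged a value important, and not only how often the abnormality occurred. The abnormalities affected are known risks of the drug. Because the planned safety evaluation rests on reported toxicities, a reader of the results could not tell how much had been left out.

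**Working it through.** **1. Which findings are captured without judgement?** The action rules are set beside the AE rule below. Any finding that is actually treated, for example with growth factor under Section 3.5, also qualifies as an intervention.

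| Finding | Action rule | Capture as an AE |
|---|---|---|
| Day 1 ANC < 1,500 or platelets < 75,000 | Delay (3.3.3) | Certain |
| Grade 4 neutropenia of more than 7 days, or Grade 3 with fever or infection, in the dosing period | Dose change (3.3.4) | Certain |
| Afebrile Grade 4 neutropenia of 7 days or less, no infection, recovered by Day 1 | Not listed in 3.3.4 | Judgement, unless treated |
| Leukopenia, lymphopenia, anaemia | No threshold in 3.3.3 or 3.3.4 | Judgement, unless treated |
| Related Grade 3 liver test in the dosing period | Dose change (3.3.5) | Certain |
| Related Grade 2 liver test | Reduction only if the investigator thinks it needed (3.3.5) | Judgement, unless acted on |
| Grade 1 liver test | None | Judgement |

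The scheduled on-treatment counts fall on Day 1, when the retreatment thresholds apply. Section 3.3.4 defines Grade 4 neutropenia as ANC below 500. That is below 1,500, so a Grade 4 value at a scheduled count that governs retreatment delays the cycle. The short Grade 4 episode in the third row can therefore be seen only on an unscheduled draw.

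**2. The Section 4.1.2 example.** That section describes a white count of 1000/mm³ "to less than 2000 is considered Grade 3 (severe) but may not be considered serious". ANC cannot exceed the white count. With a white count below 1,500, ANC must be below 1,500 and the cycle is delayed. With a white count from 1,500 to just under 2,000, ANC reaches 1,500 only if neutrophils make up at least 1,500 / white count, which is more than 1,500 / 2,000 = 75%. On Day 1, then, a patient with this value will usually be captured through neutropenia. What may be lost is the leukopenia entry itself.

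**3. Size.** The plan states no cytopenia or liver-test rate, so there is no figure to reproduce. As an illustration:

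reported rate = t × [1 − m(1 − s)]

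Here t is the true proportion of patients with the abnormality, m the share of those patients whose values prompted no action, and s the share of that group still judged significant. All three are assumptions. With t = 0.40 and 53 patients (53 × 0.40 = 21.2 affected), the reported rate and the expected number of patients missed, 53 × t × m(1 − s), are:

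| m | s = 0 | s = 0.5 | s = 0.9 | s = 1 |
|---|---|---|---|---|
| 0.1 | 36% (2.1) | 38% (1.1) | 39.6% (0.2) | 40% (0) |
| 0.5 | 20% (10.6) | 30% (5.3) | 38% (1.1) | 40% (0) |
| 0.7 | 12% (14.8) | 26% (7.4) | 37.2% (1.5) | 40% (0) |

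The fraction lost, m(1 − s), does not depend on t. At m = 0.5 the range is 10% to 20% for t = 0.20, and 30% to 60% for t = 0.60. Since m(1 − s) cannot be negative, the effect is downward or nil.

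**The case against.** The strongest reply is that the rule already has a route requiring no action. The investigator may call any value clinically significant, Section 4.2 points the same way, and a competent investigator would be expected to record a Grade 4 neutropenia. That defeats the inference that every value without action is dropped. It does not remove the dependence on judgement, because neither section sets a grade at which recording is required.

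Second, the retreatment thresholds apply on the days when counts are scheduled, so the clinically important neutropenia and thrombocytopenia seen then are captured. This stands. It rules out saying that most cytopenias trigger nothing, for which the documents give no figure in any case.

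Third, the general Grade 4 sentence in Section 3.3.5 could be read to cover blood counts. It sits under the non-haematological heading and, read broadly, conflicts with the duration conditions in Section 3.3.4. It cannot be relied on to close the gap until the two are reconciled.

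Fourth, the stakes are limited. Toxicity is a descriptive secondary objective, no numerical toxicity stopping boundary uses these rates, and the laboratory values are collected as safety data anyway. That is fair. It lowers the priority, and it also makes the remedy cheap.

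**Conclusion.** The point holds as a limited one. Some laboratory toxicities can be left out of the AE-based rates at any grade if they prompt no action and the investigator does not call them significant, and no planned table would show this. The exposed findings are leukopenia, lymphopenia, untreated anaemia, Grade 1 and unacted Grade 2 liver tests, and low counts on unscheduled draws that recover by Day 1. Their overall rates may be understated. By how much, or whether at all, depends on two shares that the documents do not give; under the assumptions shown, a true 40% could be reported as anything from 12% to 40%.

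A reader might go further and infer that the rate of the drug's dose-limiting toxicity is biased low. The documents do not support that. Toxicity that limits dosing leads to delay, modification or discontinuation and so meets the AE rule. Nor do they support near-total under-reporting of lymphopenia and leukopenia: that would require investigators almost never to judge such values significant, and nothing in the plan says so.

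This is a worthwhile, inexpensive improvement to reporting. It does not affect the primary endpoint or the two-stage decision.

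**What to change.** Keep the AE rule in Section 4.1.1. Add to Section 5.5 text to this effect:

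> All collected CBC, AST, ALT, bilirubin, electrolyte and creatinine results, scheduled and unscheduled, will be graded by CTCAE 4.03 directly from the laboratory values. The worst grade per patient will be tabulated for all treated patients, whether or not the value was assessed as an AE.

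The denominator should be all treated patients. The evaluable set in Section 3.1 requires a completed cycle and a documented radiographic response, and so could leave out patients who stop early for toxicity.

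The cost is one sentence and one derived table, with no new sampling and no change in patient management. This assumes that the results, including unscheduled ones, are held in a form that can be analysed; if not, they must be extracted. Reported laboratory toxicity rates will probably look somewhat higher.

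Two limits remain. Low points between visits that nobody sampled will still be missed. With unscheduled results included, the worst grade also depends on how often a patient was sampled.

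Separately, the sponsor should reconcile the Grade 4 wording in Sections 3.3.4 and 3.3.5, because whether a short Grade 4 cytopenia leads to action, and so becomes an AE, depends on which is followed.
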